10.4.1 Electronic Case Report Forms

Data for this study will be recorded using an electronic CRF. Sites will receive training for appropriate CRF completion and sites will be responsible for data entry into the eCRF. In the event of discrepant data, the Sponsor or designee will request clarification from the sites. The sites will resolve discrepant data electronically in the CRF. An Immune Pharmaceuticals representative, or a designee, will perform final data review and external data reconciliations prior to all major milestones, including database close and lock. CRFs and correction documentation will be

maintained in the CRF's audit trail. Records retention for the study data will be consistent with the SOPs of the Sponsor or designee.

A CRF must be completed for each screened subject. For each screen-failed subject, the reason for screen failure will also be collected in the CRF. The corresponding forms for the activities and assessments performed should be entered into EDC for screen-failed patients. The entire casebook of data must be reviewed and electronically signed by the investigator.

11.0 STUDY ADMINISTRATION

11.1 PARTICIPATING CENTERS

Up to 10 sites in Israel and US will participate in this study. Additional sites may be added as necessary to complete enrollment. A list of the Principal Investigators will be maintained in the trial master file.

11.2 CLINICAL TRIAL SUPPLIES

The investigator and designee(s) will be responsible for administering, inventory, and accountability of all clinical trial supplies, and exercising accepted medical and pharmaceutical practices. An accurate and timely record of the disposition of all clinical supplies must be maintained. The supplies and inventory record must be made available for inspection upon request. Upon completion or termination of the study, the investigator will keep the remaining clinical supplies along with a copy of the inventory record and a record of the clinical supplies returned. Under no circumstances will the investigator allow the study drugs or other study-related supplies to be used other than as directed by this protocol.

11.3 INVESTIGATOR SITE FILE

All documents required for the conduct of the study as specified in the ICH-GCP guidelines will be maintained by the investigator in an orderly manner and made available for monitoring and/or auditing by the Sponsor and regulatory agencies.

11.4 FINAL REPORT

A final study report will be prepared after the study has been completed and database has been cleaned, locked and analyzed. The report will be prepared according to the ICH E3 guidelines.

11.5 RETENTION OF STUDY RECORDS

The investigator will retain study documents until at least 2 years after the last approval of a marketing application in an ICH region and until there are no pending or contemplated marketing applications in an ICH region or at least 2 years have elapsed since the formal discontinuation of clinical development of the investigational product. However, these documents should be retained for a longer period if required by the applicable regulatory requirement(s) or if needed by the Sponsor. If the investigator is unable to retain the study documents for the required amount of time, Sponsor or designee must be informed of the individual who will be assuming this responsibility.

These files must be made available for inspection upon reasonable request by authorized representatives of Sponsor and/or the relevant regulatory agencies.

11.6 CONFIDENTIALITY AND PUBLICATION

Study patient medical information obtained by the study is confidential and disclosure to third parties other than those noted below is prohibited. Throughout the study, all data will be identified only by the subject number, and where applicable, the study patient's initials and birthdate.

At the study patient's request, medical information may be given to his or her personal physician or other appropriate medical personnel responsible for his or her welfare. The personal physician will be notified by site personnel of study patient participation in the study.

All information supplied by Immune Pharmaceuticals, Inc. in association with this study and not previously published, is considered confidential information. This information includes, but is not limited to, the Investigator's Brochure, the protocol, CRFs, and other scientific data. Any data collected during the study are also considered confidential. This confidential information shall remain sole property of Immune Pharmaceuticals, shall not be disclosed to others without the written consent of Immune Pharmaceuticals, and shall not be used except in the performance of this study.

The information developed during the conduct of this study is also considered confidential, and will be used by Immune Pharmaceuticals, Inc. This information may be disclosed as deemed necessary by Immune Pharmaceuticals, Inc. To allow the use of this information derived from this study, the investigator is obliged to provide Immune Pharmaceuticals with complete test results and all data developed in this study.

Appendix A: Schedule of Activities

Study Procedures	Screen ing	l .	reatme Period			F	ollow-	up Pei	rioda		Early Discontinu ation ^b
Visit	1	2	3	4	5	6	7	8	9°	Phon e call	-
Study Day (visit window +/- 2 day)	-28 to - 1	0	14 (+/- 2)	28 (+/- 2)	42 (+/- 2)	56 (+/- 2)	70 (+/- 2)	84 (+/- 2)	118 (+/- 2)	Appr ox. days 144 and 204	-
Informed consent	X										
Inclusion/exclusion criteria	X	X									
Demographic & medical history	X										
Karnofsky performance status	X										
Physical examination ^c	X ^c	X*	X*	X*	X	X	X	X			X
Vital signs	X	X^d	Xd	Xd	X	X	X	X			X
ECG	X							X			X
Hematology (including eosinophil count) and biochemistry ^e	X ^f	X*	X*	X*	X			Х			Х
Serum eotaxin-1		X*	X*	X*	X	X	X	X			X
Screen for active/latent tuberculosis ^{, g}	X										
Skin punch biopsy for H&E and eosinophil count	X				X ^h						
Skin punch biopsy for DIF on salt split skin	X										
IIF and BP180 & BP230 auto antibodies	X ^j	X*	X*	X*	X	X	X	X			X
Assessment of BP severity	X										
Serology (HIV, HBV, HCV, CMV) e	X										
Urine β-hCG ⁱ		X*	X*	X*	X			X			
Anti-bertilimumab antibodies		X*	\mathbf{X}^*	X*	X	X	X	X			X
PK (bertilimumab) blood sampling		X^k	Xk	X ^k	X	X	X	X			X
PBMC biomarker blood sampling		X*			X						
Semen analysis		X^{l}	Xl	Xl					X		X ^m
Bertilimumab infusion		X	X	X							
BPDAI (including Pruritus evaluation) and lesion	X**	X*	X*	X*	X	X	X	X			X
healing assessment	V-4-4	v*	X*	X*	37	v	37	17	-		77
ABQOL questionnaire Corticosteroid management	X**	X*	X	X	X	X	X	X	v	v	X
Prior and concomitant medications	X	X X*n	X*n	X*n	X	X	X	X	X	X	X
Adverse events	X	X*n	X*n	X*n	X	X	X	X	X	X	X
Infusion reaction assessment	37	X°	X°	X°	77	**	***	***	-		***
Photography	X	X*	X*	X*	X	X	X	X	l	1	X

Note: Ability to taper steroids during scheduled or unscheduled visits will be determined by the investigator based on patient

62

response.

- * Denotes assessment will be done pre-dose
- ** To be performed if possible prior to commencement of corticosteroid regimen
- ^a Visits 3 through 9 have a ±2 day window. The window is calculated from the actual visit day compared to baseline (Day 0), (e.g., for Visit 6 (Day 56) the window would be Day 54 to Day 58).
- ^b At this visit, the activities to be performed will relate to the study period at which time the patient discontinued.
- ^c Physical examination including weight; height measurement at screening only.
- ^d Vital signs will be measured pre-dose (any time prior to the initiation of treatment infusion), immediately at the completion of treatment infusion (approximately 30 minutes after initiation) and approximately 2 hours following initiation of treatment infusion.
- ^e Clinical laboratory assessments will be performed by a local laboratory for the screening visit and a central laboratory for every subsequent visit.
- ^fBiochemistry will include serum β-hCG at screening for females of childbearing potential only.
- g The patient should be evaluated for active/latent TB as applicable (e.g., PPD, QFT, and/or chest x-ray)
- h The Visit 5 (Day 42) punch biopsies should be taken in the area of the previous biopsies, as much as possible.
- ⁱFemales of childbearing potential only.
- ^j IIF only at screening
- ^k Blood samples for bertilimumab (PK analysis) will be collected pre-dose and at the completion of treatment infusion (approximately 30 minutes after the initiation) and 2 hours following the initiation of treatment infusion. PK samples 30 minutes post-infusion should be taken as close to this time as possible.
- ¹Semen analysis will be performed for males pre-dose and close to the completion of infusion as possible. Pre-dosing samples can be taken up to 2 days prior to dosing.
- ^m Only for males with abnormal semen analysis results from Day 0, Day 14 or Day 28 compared to pre-dose value at Visit 2 (Day 0)
- ⁿ Adverse events and concomitant medication information to be recorded pre-dose and 2 hours after the initiation of infusion.
- ^o Infusion reactions should be assessed at the completion of infusion (approximately 30 minutes after the initiation) and 2 hours following the initiation of treatment infusion.

Protocol: Immune/BRT/BP-01 Page 63 of 72 Final Version 8.0 February 28, 2018

63

Appendix B: Assessment of BP Severity*

*Assessment to be done on three occasions during the screening period

Date of Assessment	Assessor Initials	Number of bullae that are present at the time of the assessment	Number of urticarial plaques that are present at the time of the assessment	BP Severity
				☐ Moderate
				☐ Extensive
				☐ Other
				☐ Moderate
				☐ Extensive
				☐ Other
				☐ Moderate
				☐ Extensive
				□ Other
				☐ Moderate
				☐ Extensive
				□ Other
				☐ Moderate
				☐ Extensive
				□ Other
				☐ Moderate
				☐ Extensive
				□ Other
				☐ Moderate
				☐ Extensive
				□ Other

Appendix C: Karnofsky Performance Status

KARNOFSKY PERFORMANCE STATUS SCALE DEFINITIONS RATING (%) CRITERIA

Able to carry on normal activity and to work;	100	Normal no complaints; no evidence of disease.
No special care needed.	90	Able to carry on normal activity, Minor signs or symptoms of disease.
	80	Normal activity with efforts; some signs or symptoms of disease.
Unable to work; able to live at home and care for most personal needs; varying amount of assistance needed.	7 0	Cares for self; unable to carry on normal activity or to do active work.
amount of assistance needed.	60	Requires occasional assistance, but is able to care for most of his personal needs.
	50	Requires considerable assistance and frequent medical care.
Unable to care for self; Requires equivalent of institutional or hospital care; diseases may be progressing	40	Disabled; requires special care and assistance.
rapidly.	30	Severely disabled; hospital admission is indicated although death not imminent.
	20	Very sick; hospital admission necessary, Active supportive treatment necessary.
	10	Moribund; fatal processes progressing rapidly.
	0	Dead

Oxford Textbook of Palliative Medicine, Oxford University Press. 1993;109.

Appendix D: Bullous Pemphigoid Disease Area Index [1]

BPDAI					
SKIN	ACTIVITY		ACTIVITY		DAMAGE
Anatomical location	Erosions/Blisters	Number of Lesions if <3	Urticaria/ Erythema / Other	Number of Lesions if <3	Pigmentation Other
	0 absent		0 absent		Absent 0, present 1
	1 1-3 lesions, none > 1 cm diameter		1 1-3 lesions, none >6 cm diamter		
	2 1-3 lesions, at least one > 1 cm diameter		2 1-3 lesions, at least one lesion > 6 cm diameter		
	3 >3 lesions, none > 2 cm diameter	-	3 >3 lesions, or at least one lesion > 10 cm diameter		
	5 >3 lesions, and at least one >2 cm		5 >3 lesions and at least one lesion > 25 cm diameter		
	10 >3 lesions, and at least one lesion >5 cm diameter or entire area		10 >3 lesions and at least one lesion > 50 cm diameter or entire area		
Head					
Neck	J				
Chest					
Left arm)				
Right arm	1 =		1		
Hands	1 = 1		Jr		
Abdomen			les -		
Genitals					
Back/Buttocks	i				
Left leg					
Right leg					
Feet	1 = 1				
Total skin	/120		/120		
MUCOSA	Erosions/Blisters				
	1 1 lesion				
	2 2-3 lesions				
	5 >3 lesions, or 2 lesions >2cm			_	
	CONTRACTOR OF STREET				
	10 entire area				
Eyes					
Nose					
Buccal mucosa					
Hard palate					
Soft palate					
Upper gingiva					
Lower gingiva					
I ongue					
Floor of Mouth	+				
Labial Mucosa	4 ===				
Posterior	S-				
Pharynx					
Anogenital		-		-	
Total Mucosa					

TOTAL ACTIVITY SCORE	TOTAL DAMAGE SCORE

BPDAI Pruritus Component- VAS

□ Baseline □ Beginning Consolidation

 $\ \square$ Consolidation phase $\ \square$ End of Consolidation

Tapering phase
 Partial remission on minimal therapy

Complete remission on minimal therapy
 Partial remission off therapy

□ Complete remission off therapy □ Flare

A. How severe has your itching been over the last 24 hours?

0 1 2 3 4 5 6 7 8 9 10 None

Score out of 10=

B. How severe has your itching been over the past week?

0 1 2 3 4 5 6 7 8 9 10 None Severe

Score out of 10=

B. How severe has your itching been over the past month

0 1 2 3 4 5 6 7 8 9 10 None Severe

Score out of 10=

Average INTENSITY SCORE FOR PAST MONTH = (A+B+C)=

OR.

For BP patients with impaired mental functioning:

No evide	nce of itch (no excoriations)	0
Mild itch	(isolated excoriations up to two body sites)	10
Moderate	eitch (excoriations on ≥ 3 body sites, impairment of daily activity)	20
Severe it	ch (generalized excoriations, sleep impairment)	30
	TOTAL	

TOTAL SCORE /30

@University of Pennsylvania 2011

Appendix E: Autoimmune Bullous Disease Quality of Life

ABQOL Questionnaire

1	Not Done, specify reason:				
	Date of Assessment			(dd Month yyyy)	
L					
1.	In regards to your blistering disease, does your skin burn, strong or hurt in any way?	ing	3 All the to 2 Sometim 1 Occasion 0 Never	nes	
2.	In regards to your blistering disease, does your skin itch?		3 All the to 2 Sometim 1 Occasion 0 Never	nes	
3.	Have you had to change your clothing because of your blister disease?	ring	clothing is have had to 2 I have had to 1 I have had	be very careful with how tight my and what materials they are made of – o change what I wear all the time ad to change most of the things I wear ad to change some of the things I wear ever had to change what I wear	I
4.	Do you notice your skin heals slowly?		2 I notice to	this all the time this sometimes this occasionally ever had this problem	
5.	Do you have difficulty bathing showering because of your blistering disease?	0	3 All the to 2 Sometim 1 Occasion 0 Never	nes	
6.	In regards to your blistering disease, does your mouth have erosions which are painful?		3 All the to 2 Sometim 1 Occasion 0 Never	nes	

7. In regards to your blistering disease, do your gums bleed easily?	 3 All the time 2 Sometimes 1 Occasionally 0 Never
8. Does your blistering disease result in you having to avoid food or drinks that you enjoy?	 3 I can no longer eat any of the foods I used to enjoy 2 I can eat some of the foods I enjoy 1 I can eat most of the foods I enjoy 0 I can eat anything I like
9. As a result of your blistering disease, are you embarrassed about your appearance?	 3 All the time 2 Sometimes 1Occasionally 0 Never
10. Do you feel depressed or angry because of your blistering disease?	 3 All the time 2 Sometimes 1 Occasionally 0 Never
11. Do you feel anxious or cannot relax as a result of your blistering disease?	 3 All the time 2 Sometimes 1 Occasionally 0 Never
12. Do you worry that friends and family find your blistering skin condition tiresome?	 3 All the time 2 Sometimes 1 Occasionally 0 Never
13. Is your blistering disease causing sexual difficulties?	 3 All the time 2 Sometimes 1 Occasionally 0 Never

14. Does your blistering disease affect relationships with friends or loved ones?	 3 I have had to end a relationship because of my disease OR I cannot have a relationship because of my disease 2 Relationships are very difficult 1 Relationships are a little difficult 0 This has not affected my relationships
15. Does your blistering disease affect your social life?	 3 I cannot go out to socialize any more 2 I can only go to some social events 1 I can go to most social events 0 My social life is not affected
16. Does your blistering disease affect your work or study?	 3 Yes, I can no longer work or study 2 Yes, I find it difficult to work or study 1 Yes, it is a little harder than before to work or study 0 No, I am not affected OR N/A
17. Do employers discriminate against you because of your blistering disease?	 3 I cannot find a job due to my blistering disease 2 I have had to change jobs due to my blistering disease 1 I still have my job but it is more difficult than before 0 My employers are completely understanding OR N/A

Appendix F: Topical Steroids Potency Class Table

Class	Generic Name	Formulation
Class 1 Very High Potency		
	Betamethasone dipropionate	0.05% G O (diprolene)
	Clobetasol	0.05% C F G L O
	Diflorasone diacetate	0.05% O
	Halobetasol propionate	0.05% C O
Class 2 High Potency		
	Amcinonide	0.1% O
	Betamethasone dipropionate	0.05% C (diprolene)
	Desoximetasone	0.05% G, 0.25% C O
	Fluocinonide	0.05% C G O S
	Halcinonide	0.1% C
	Mometasone furoate	0.1% O
Class 3 High Potency		
	Amcinonide	0.1% C L
	Betamethasone dipropionate	0.05% C (non-diprolene)
	Betamethasone valerate	0.1% O
	Desoximetasone	0.05% C
	Diflorasone diacetate	0.05% C
	Fluticasone propionate	0.005% O
	Halcinonide	0.1% O S
	Triamcinolone	0.1% O
Class 4 Mid Potency		
orace v mile v eleney	Betamethasone valerate	0.12% F
	Flucinolone acetonide	0.025% O
	Flurandrenolide	0.05% O
	Hydrocortisone valerate	0.2% 0
	Mometasone furoate	0.1% C
	Triamcinolone	0.1% C
Class 5 Mid Potency	THATICATOR	0.120
Class 5 mid 1 otoricy	Betamethasone dipropionate	0.05% L
	Betamethasone valerate	0.1% C
	Flucinolone acetonide	0.025% C
	Fluticasone propionate	0.05% C
	Flurandrenolide	0.05% C
	Hydrocortisone butyrate	0.1% C
	Hydrocortisone valerate	0.2% C
Class 6 Low Potency	riyuruculusure valetate	0.2.0 0
Oldoo O LOW POLETICY	Alcometasone dipropionate	0.05% C O
	Betamethasone valerate	0.1% L
	Desonide	0.1% L 0.05% C L O
	Flucinolone acetonide	0.01% C S
Close 7 Law Potence	r lucinoidrie acetorilde	0.0170 0 3
Class 7 Low Potency	Lhudro orticono contete	0.5% 0.1.0.4% 0.0.5
	Hydrocortisone acetate	0.5% CLO, 1% COF
	Hydrocortisone hydrochloride	0.25% C L, 0.5% C L O S, 1% C L O S, 2% L, 2.5% C L O S

C = Cream, F = Foam, G = Gel, L = Lotion, O = Ointment, S = Solution

Source: Dermatol Nurs @ 2006 Jannetti Publications, Inc.

# **Version History**

Version Number	Date	Revision		
0.1	April 16, 2018	Draft		
0.2	July 11, 2018	Draft		
0.3	September 16, 2018	Draft		
0.4	November 28, 2018	Draft		
0.5	December 4, 2018	Draft		
0.6	January 28, 2019	Draft		
0.7	January 31, 2019	Draft		
1.0	February 6, 2019	Final		

## **List of Abbreviations**

ABQOL	The Autoimmune Bullous Diseases Quality of Life
AE	Adverse Event
B-hCG	Human beta chorionic gonadotropin
BMI	Body Mass Index
BP	Bullous Pemphigoid
BPDAI	Bullous Pemphigoid Disease Area Index
CMV	Cytomegalovirus
CRF	Case Report Form
CS	Clinically Significant
DIF	Direct Immunofluorescence
ECG	Electrocardiography
ECP	Eosinophil Cationic Protein
HBV	Hepatitus B Virus
HCV	Hepatitus C Virus
Н&Е	Hematoxylin & Eosin
HIV	Human Immunodeficiency Virus
IIF	Indirect Immunofluorescence
NCS	Non-Clinically Significant
PBMC	Peripheral Blood Mononuclear Cell
PD	Pharmacodynamics
PK	Pharmacokinetics
PPD	Purified Protein Derivative
QFT	Quantiferon Test
SAE	Serious Adverse Event
SAP	Statistical Analysis Plan
SOC	System Organ Class
TB	Tuberculosis
VAS	Visual Analogue Scale

### 1 Introduction

### 1.1 General

Bertilimumab is the first monoclonal antibody to specifically neutralize human eotaxin-1 (eotaxin). Bertilimumab has been shown to inhibit eotaxin-stimulated migration of cells and may therefore be useful in the treatment of human diseases such as Bullous Pemphigoid (BP), where eosinophil accumulation is an important feature.

The purpose of this study is to provide proof of concept for the treatment of BP with bertilimumab. This study will provide both safety and efficacy data for internal decision-making regarding further development of bertilimumab in BP. Its efficacy in newly diagnosed patients would be proven by allowing reduced initial doses of corticosteroids and a reduced cumulative dose of corticosteroids by facilitating rapid tapering to 10 mg prednisone equivalent or lower after initial control of BP lesions. Its efficacy in patients resistant to corticosteroid tapering would be proven by allowing patients to be tapered down from corticosteroids without flaring and/or allowing smaller doses of oral corticosteroids to control the disease.

The study will investigate newly diagnosed adult patients and adult patients resistant to corticosteroid tapering with moderate to extensive BP. The treatment period will include three IV infusions of 10 mg/kg bertilimumab on study Days 0, 14 (±2 days) and 28 (±2 days) and a follow-up period up to Day 84 (or Day 118 for males who have had abnormal semen analysis results on Day 0, Day 14 or Day 28) relative to pre-dose Visit 2. Patients will receive concomitant oral steroids during the treatment and follow-up period.

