8.0 STATISTICAL ANALYSIS

This is an open-label study. Thus, only descriptive statistics are planned. All data collected on the case report forms (CRFs) will be summarized for the clinical study report (CSR).

All continuous parameters will be summarized using standard summary statistics as appropriate (n, mean, standard deviation, median, minimum, maximum, 25th percentile, and 75th percentile).

Summary statistics for categorical variables will include frequency counts and percentages. Summaries will be presented for all patients and by Treatment Phase and Follow-up Evaluation.

Details will be specified in the statistical analysis plan.

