## 4 Treatment Groups

This is a single arm trial, where all eligible patients will be treated with investigational product - Bertilimumab.

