### **6.2.2 Efficacy Population**

The Efficacy population will be a subset of the Safety population. All patients in the Efficacy population will have the visit score on the Bullous Pemphigoid Disease Area Index (BPDAI) at baseline and at least one post baseline BPDAI score.

"Baseline" is defined as the last measurement obtained before the treatment initiation.

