### 9.4 Efficacy

All efficacy analyses will be done on efficacy population.

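### SAP 1.1 states a separate efficacy criterion for newly diagnosed and for taper-resistant patients, but no planned summary is split by patient type

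*SAP*

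**What the plan says.** SAP 1.1 (General), repeating Protocol 1.3 (Study Rationale), gives two criteria.

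- Newly diagnosed: the criterion opens "Its efficacy in newly diagnosed patients would be proven by" and names a lower starting dose and a lower total steroid dose, through a quick taper to 10 mg prednisone equivalent or below once lesions are first controlled.
- Resistant to tapering: "Its efficacy in patients resistant to corticosteroid tapering would be proven by allowing patients to be tapered down from corticosteroids without flaring". The alternative it names is disease control on a lower oral steroid dose.

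The analysis sections treat everyone alike. SAP 6.2.2 states: "The Efficacy population will be a subset of the Safety population". Membership depends only on having a baseline and a later BPDAI score. SAP 9.4 states: "All efficacy analyses will be done on efficacy population". The BPDAI and prednisone outputs (9.4.1), the pruritus, ABQOL and flare outputs (9.4.2) and the PD outputs (9.6) name no split by type. SAP 9.2 lists demographics, Karnofsky status, medical history and screening tests, but not patient type. Protocol 8.0 is also pooled: "Summaries will be presented for all patients and by Treatment Phase and Follow-up Evaluation".

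Some patient-level output is planned: listings of all CRF data (SAP 10), a by-subject steroid listing (SAP 9.3.2), subject-level presentation of control of disease activity (SAP 7.2.2), and individual narratives (Protocol synopsis, Statistical Methods).

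**The concern.** The two types differ by design, so a pooled summary mixes unlike patients.

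- **Steroids at entry.** Protocol 6.8.1 caps the prior dose and sets Day 0 conditions for newly diagnosed patients. It requires no wash-out for resistant patients and allows them other regimens. Protocol 6.8.3 restricts Class 1 and 2 topical steroids for newly diagnosed patients only.
- **Expected course.** Protocol 1.1 says steroids alone can control lesions rapidly. Newly diagnosed patients may therefore improve on steroids begun around entry, whereas resistant patients enter because tapering has not worked.
- **Reference visit.** Protocol 2.2 measures change in the clinical scores from Screening in resistant patients and from Visit 2 in newly diagnosed patients.

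SAP 1.1 says the data serve internal decisions on further development. A pooled mean or response rate can look acceptable while one type does poorly, and the reader could not tell how many patients of each type lie behind it.

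**Working it through.** The documents contain no sample-size, power or precision figure to reproduce. The check sets the criteria beside the outputs and then asks what a pooled count can reveal.

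**1. Criterion against output**

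| Type | Criterion (SAP 1.1) | Nearest planned summary | What it shows |
|---|---|---|---|
| Newly diagnosed | Lower initial and cumulative dose, rapid taper to 10 mg or below | Mean and cumulative dose by visit; Visit 8 dose of 10 mg/day or less (SAP 7.2.1, 9.4.1) | Both types together |
| Resistant | Taper without flare, or control on smaller doses | The same dose tables; flares by visit (SAP 9.4.2) | Both types together; flare not linked to taper |

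**2. What a pooled count identifies**

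Inputs: up to 15 patients (Protocol synopsis). The 9 successes and the splits are assumptions, since the documents give neither. Let n_N and n_R be the numbers newly diagnosed and resistant. With 9 pooled successes, the newly diagnosed successes can lie anywhere from max(0, 9 − n_R) to min(n_N, 9).

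| Assumed split n_N / n_R | Range of n_N successes | One extreme | Other extreme |
|---|---|---|---|
| 5 / 10 | max(0, −1) = 0 to 5 | 0/5 and 9/10 | 5/5 and 4/10 |
| 9 / 6 | max(0, 3) = 3 to 9 | 3/9 and 6/6 | 9/9 and 0/6 |
| 12 / 3 | max(0, 6) = 6 to 9 | 6/12 and 3/3 | 9/12 and 0/3 |

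Every row pools to 9/15 = 60%. The pooled figure does not identify either type's result.

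**3. The common dose rule**

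SAP 7.2.1 counts a Visit 8 mean dose of 10 mg/day or less as success, whatever the starting dose. Following the recommended Table 1 in Protocol 6.8.1, a patient at 30 mg/day reaches 10 mg/day after (30 − 10)/5 = 4 weekly steps. From an assumed 60 mg/day it takes (60 − 10)/5 = 10 steps. A patient entering at 10 mg/day or less already meets the limit. Visit 8 is at 84/7 = 12 weeks. The same success therefore represents different achievements by entry dose, and the entry-dose rules differ by type.

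**4. What a split can deliver**

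Exact (Clopper-Pearson) 95% intervals, counts assumed at about 60% success:

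| Count | 95% interval |
|---|---|
| 9/15 | 32.3% to 83.7% |
| 6/10 | 26.2% to 87.8% |
| 5/9 | 21.2% to 86.3% |
| 4/6 | 22.3% to 95.7% |
| 3/5 | 14.7% to 94.7% |

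A split makes each type's result visible. It does not make it precise.

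**The case against.** Four arguments stand against the point.

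1. **The criteria are rationale, not endpoints.** In Protocol 1.3 they follow directly on a sentence about later randomised trials and can be read as what those trials would show. The operative endpoints (Protocol 2.2, SAP 7.2) are the same for both types, and only the protocol's reference visit differs. This has weight: the criteria are not formal endpoint definitions. But SAP 1.1 omits the linking sentence and places the criteria straight after stating that this study will inform development decisions.

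2. **The SAP follows the protocol.** Protocol 8.0 promises no by-type summary, so the omission is not a deviation. That is correct, and the point is an improvement to the plan. Protocol 8.0 leaves details to the SAP and does not bar a split.

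3. **Patient-level data suffice at this size.** A reader might infer from the pooling that the study output cannot answer either question at all. The documents do not support that. With at most 15 patients, the listings, narratives and subject-level disease-control data allow review by hand. The limits are that the documents do not say patient type is a CRF field, and the steroid listing does not name it as a column. SAP 9.7 and 9.8 permit further analyses, but 9.8 runs on sponsor request. SAP 7.4 mentions a decision taken after study completion, so this SAP was itself finalised after completion. A split chosen on request at that stage is open to selective reporting.

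4. **A split would not settle the criteria.** A lower or smaller dose needs something to compare with, and SAP 4 is explicit: "This is a single arm trial, where all eligible patients will be treated with investigational product - Bertilimumab". This stands in full. The lack of a control limits the evidence more than pooling does. One type may also be very small, since the protocol version history shows resistant patients were added only in version 6.0.

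**Conclusion.** The point holds as a gap in pre-specified reporting. SAP 9.2, 9.4 and 9.6 plan no summary by patient type, so the summary tables and plots cannot show the result relevant to each criterion in SAP 1.1, and the mix they depend on is not tabulated. The size cannot be fixed from the documents. Under the assumed 9/15 and 9/6 split, resistant-patient success could be anything from 0/6 to 6/6.

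Two stronger inferences should be resisted. Splitting the tables would not prove efficacy in either type, because there is no control. Nor do the documents support formal efficacy conclusions by group: with a handful of patients per type the intervals in the working span most of the range. The difference between the protocol's type-specific reference visits and the single baseline in SAP 6.2.2 is a related but separate matter, and this conclusion does not rest on it.

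**What to change.** - **SAP 9.2:** tabulate patient type (newly diagnosed; resistant to tapering).
- **SAP 9.3.2 and 10:** flag type in the by-subject steroid listing and the other listings.
- **SAP 9.4.1 and 9.4.2:** show at least the BPDAI, prednisone-dose and flare summaries, and the associated mean plots, by type beside the overall column, as counts and descriptive statistics only. By-type display of pruritus, ABQOL and PD is optional.
- **Interpretation:** label by-type results descriptive, and state that without a control group they cannot prove a reduced or smaller steroid dose in either type.

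The programming cost is one by-variable. If type is not already a CRF field, it must be derived from the eligibility data; Protocol 5.2 provides an eligibility form, but the documents do not say whether it records type. Resistance is the investigator's judgement (Protocol 4.1), so the grouping is only as firm as that judgement. The downside is small, imprecise groups, so denominators should be shown with every percentage.
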